## 1. Introduction and rationale

Lower urinary tract symptoms (LUTS) can be divided into filling, micturition and post-void symptoms [1]. LUTS include: diurnal and nocturnal pollakiuria, urinary urgency, incontinence, hypovalid voiding, voiding hesitation, prolonged urination time, voiding dribbling and paradoxical isuria. LUTS cause disturbance and compromise quality of life [2-5]. Lower urinary tract symptoms are strongly associated with aging [2, 3], so costs and patient numbers are likely to increase with future demographic changes [3, 7].

Most older men have at least one symptom [3], however, symptoms are often mild and tolerable [5, 6, 8]. The progression of this symptomatology in each individual is very subjective, in some patients the symptoms are worsening and dynamic, for others they remain more stable over time [3].

LUTS are mainly related to bladder outlet obstruction from benign prostatic hypertrophy (BPH). [1, 4]. However, they can also be related to bladder and urinary tract abnormalities, such as anatomical or functional abnormalities (detrusor hyperreactivity, urinary infections, neoplasms, lithiasis) [3, 9]. Prostatic hypertrophy is due to hyperplasia of both the epithelial and stromal components and originates in the periurethral region of the gland. In the initial stages, there is a development of micronodules of stromal and glandular tissue in the periurethral area; over the years these nodules increase in size by compressing and distorting the prostatic urethra, hindering the urinary flow. Hormonal, immune, dietary, neurological and genetic factors are involved in the genesis of BPH. An alteration of the balance at a local level between estrogens and androgens is recognized. This phenomenon increases the ability to capture testosterone which stimulates cell growth and therefore prostatic hyperplasia. Glandular growth, i.e. of the adenoma, causes both urethral compression and peripheral compression of the remaining part of the parenchyma. This situation causes an intraglandular inflammatory picture which results in asymptomatic abacterial chronic prostatitis which can be found at the histological level of patients undergoing endoscopic resection of prostate adenoma. This inflammation aggravates and worsens the underlying urinary symptoms. According to European guidelines (UAE), the diagnosis of BPH must make use of a complete anamnestic collection to know any comorbidities of the patient. It must make use of the use of questionnaires to be submitted to each patient (e.g. IPSS, International Prostate Symptom Score), with the aim of quantifying voiding symptoms and monitoring worsening/improvements over time after medical therapy [10]. The patient should maintain a voiding diary to evaluate micturition characteristics, including voided volume in 24 hours, voiding frequency, and fluid intake. It is important for the

doctor to perform an objective examination of the patient, abdominal and genital, including rectal exploration to evaluate the prostate volume, consistency, any irregularities and tenderness. Urinalysis with urine culture should be included in the primary evaluation of any patient with LUTS to identify conditions such as urinary tract infections (UTIs), microhematuria, and diabetes mellitus. It is important to determine the PSA (prostate specific antigen), a protease produced exclusively by prostatic epithelial cells, as it has a good positive predictive value since it increases in the course of both benign and malignant prostate diseases. In fact, it increases with the increase in the volume of the gland, increases in the course of inflammatory processes and in the course of prostate adenocarcinoma. Second level tests will have to be performed to make a correct differential diagnosis between these pathologies having a different therapeutic approach. The normal reference PSA value is <4 ng/ml and can be associated with its ratio (ratio between free PSA and total PSA, the higher it is, the more likely it is to be a benign disease).

Kidney function can be assessed by serum creatinine and estimated glomerular filtration rate (eGFR). Hydronephrosis, renal insufficiency or urinary retention are more frequent in patients suffering from BPH. One study reported that 11% of men with LUTS had renal insufficiency [11]. Uroflowmetry is a non-invasive urodynamic (time-volume) test widely used and recommended by guidelines for the initial diagnosis of LUTS. The parameters to consider are: Qmax, voided urine volume and flow morphology. These parameters, to be considered optimal, must be obtained when the volume of urine emptied remains between 150 and 400 ml. The morphology of the flow is "bell" shaped with a  $Q_{max} > 15$  ml/s as a rule. A curve with a flattened and lengthened morphology over time is pathological.

Uroflowmetry is limited as a diagnostic test because it cannot provide a diagnosis of the underlying disease but can be used for monitoring treatment outcomes and for correlating symptoms with objective findings [12].

With regards to imaging, renovesical ultrasound is recommended if, in addition to the LUTS mentioned above, there is hematuria or a history of kidney stones. Prostate ultrasound can be performed suprapublically or transrectally; it is essential to perform if surgery for BPH is planned, as the calculation of the prostate volume can decide which therapeutic procedure to perform [13]. The prostatic volume calculated by the suprapubic approach appears to be overestimated compared to that by the transrectal approach. Diagnostic cystoscopy is not recommended in patients with BPH.

Treatment of obstructive prostatic hypertrophy can be classified into three types:

- watchful waiting

-Pharmacological treatment

-surgical treatment

The choice of therapy is based on the severity/severity of symptoms estimated by the IPSS questionnaire.

In the presence of an IPSS score  $< 8$ , watchful waiting is possible (pharmacological therapy is not indicated). When the IPSS score  $> 8$ , it is indicated to start pharmacological therapy according to international guidelines. Surgery is confined to patients who do not respond to drug therapy and/or develop complications of an obstructive nature: obstructive renal failure, bladder stones with recurrent urinary tract infections, recurrent macroscopic haematuria.

Pharmacological treatment of prostatic hypertrophy mainly consists of alpha-blocker drugs, 5 alpha reductase inhibitors and herbal medicines.

$\alpha 1$ -blockers (e.g. tamsulosin, alfluzosin) aim to inhibit the effect of norepinephrine released on the smooth muscle cells of the prostate and thus aim to reduce the tone of the prostate and bladder neck [14]. These drugs also act on other receptors in other parts of the body, such as blood vessels, resulting in adverse effects, such as hypotension.

The different  $\alpha 1$ -blockers available on the market have similar efficacy in appropriate doses [16]. The effects take a couple of weeks to develop completely burned, but significant efficacy versus placebo can occur within hours or days [15].

Controlled studies show that  $\alpha 1$ -blockers typically reduce IPSS by approximately 30-40% and increase Qmax by approximately 20-25% [17].  $\alpha 1$ -blockers do not reduce prostate size [18]. The most frequent adverse events of  $\alpha 1$ -blockers are asthenia, dizziness and orthostatic hypotension. They do not negatively affect libido, have a small beneficial effect on erectile function, but sometimes cause abnormal ejaculation [19]. Originally, abnormal ejaculation was associated with retrograde ejaculation, but more recent data show that it is due to a decrease or absence of seminal fluid during ejaculation.

Thus,  $\alpha 1$ -blockers are often considered the first-line pharmacological treatment of LUTS due to their rapid action, good efficacy, low frequency and severity of adverse events. However,  $\alpha 1$ -blockers do not prevent the onset of acute urinary retention and the need for surgery for BPH.

Another category of drugs involved in the treatment of BPH are the 5 alpha reductase inhibitors (5-ARIs). The effects of androgens on the prostate are mediated by dihydrotestosterone (DHT), which is converted from testosterone by the enzyme 5 $\alpha$ -reductase. There are two isoforms of this enzyme:

- 5 $\alpha$ -reductase type 1, activity predominant in extraprostatic tissues, such as skin and liver.

- 5 $\alpha$ -reductase type 2, predominant in the prostate.

Two 5-ARIs are available for clinical use: dutasteride and finasteride. Finasteride inhibits type 2 5 $\alpha$ -reductase only, whereas dutasteride inhibits type 1 and type 2 5 $\alpha$ -reductase with similar potency. 5 $\alpha$ -reductase inhibitors work by inducing apoptosis of prostate epithelial cells [20] leading to a reduction in prostate size by approximately 18-28% and a decrease in circulating PSA levels by approximately 50% after six to twelve months of treatment [21].

Placebo-related clinical effects are observed after a minimum treatment duration of at least six to twelve months. An indirect comparison and a direct comparative trial (twelve months duration) indicate that dutasteride and finasteride are equally effective in the treatment of LUTS [21, 23]. The greater the baseline prostate volume, the greater the symptomatic benefit of dutasteride over tamsulosin.

5 $\alpha$ -reductase inhibitors, but not  $\alpha$ 1-blockers, reduce the long-term risk (> 1 year) of acute urinary retention or the need for surgery [22, 24].

The most notable adverse effects of 5-ARIs are related to sexual function and include decreased libido, erectile dysfunction (ED), and less frequently, ejaculation disorders such as retrograde ejaculation, ejaculation failure, or decreased semen volume [ 21]. Gynecomastia develops in 1-2% of patients.

According to guidelines (EAU), in addition to the two categories of drugs mentioned above, there are also treatments for BPH based on natural extracts (phytotherapy).

Herbal medicines are made from roots, seeds, pollen, bark or fruit. There are single herbal preparations and preparations that combine two or more plants in one tablet. The most used plants are Cucurbita pepo (pumpkin seeds), Hypoxis rooperi (South African star grass), Pygeum africanum (African plum tree bark), Secale cereale (rye pollen), Serenoa repens (dwarf palm) and Urtica dioica (roots of 'nettle). In vitro, plant extracts may have anti-inflammatory, anti-androgenic and estrogenic effects; they can inhibit aromatase, lipoxygenase, growth factor-stimulated proliferation of prostate cells,  $\alpha$ -adrenoreceptors, 5 $\alpha$ -reductase, muscarinic cholinoreceptors, dihydropyridine and vanilloid receptors, and neutralize free radicals [25-26]. Pharmacokinetic properties can vary significantly depending on how Serenoa repens is extracted.

Herbal therapeutic agents are a heterogeneous group and may contain different concentrations of active ingredients. In general, no herbal agent has been shown to reduce prostate size and a decrease in the progression of BPH has not been demonstrated [27-28]. Side effects during herbal medicine

are usually mild and comparable to placebo. Gastrointestinal disturbances are the most common reported.

Short-term studies have recently been performed on the combination of plant extracts with alpha-blockers and 5-ARIs.

PROCOMB study (2014): randomized double-blind multicenter study for 12 months of treatment in which patients were divided into 3 groups; group A, who received only Serenoa Repens + Lycopene (Ly) + Selenium (Se); group B, who received only tamsulosin 0.4 mg; group C, who received tamsulosin 0.4 mg + SerR + Ly+Se. The aim of the study was to achieve an improvement in some parameters (IPSS, post-void residual and Qmax at uroflowmetry) in patients in group C compared to those in group B. The results demonstrated a better efficacy of the combined therapy of group C compared to the single therapy of group B, (increase in Qmax and decrease in IPSS value). [29]

QUALIPROST study (2015): prospective, longitudinal, observational and multicenter study with the evaluation of 6 months of treatment. We included patients not taking any therapy, patients on monotherapy (with alpha-blockers, 5-ARIs and Serenoa Repens hexane extract) and patients on combined therapy (alpha-blockers + 5-ARIs and alpha-blockers + Serenoa Repens).

The results obtained demonstrated comparable efficacy in the use of combined therapy with alpha blocker + Serenoa repens and with alpha blocker + 5-ARI [30].

To date, there are no scientific studies in the literature that evaluate the efficacy of the treatment of BPH with Serenoa Repens extracted with CO2 and PEA (palmitoylethanolamide) (PEAPROSTIL 600, FARMITALIA®). PEA is a substance produced by all living beings with analgesic and anti-inflammatory properties. It protects cells and tissues from oxidative damage, reduces chronic pain and restores the physiological tissue balance. It was discovered in 1957 and studied by Rita Levi di Montalcini, who won the Nobel prize in 1993. This synergistic action deriving from the combined activity of Serenoa Repens and PEA can lead to a reduction of the chronic prostatic inflammatory process (chronic abacterial prostatitis) in patients with BPH. PEAPROSTIL 600 (FARMITALIA®) is a supplement that is administered in orodispersible form without the need for the use of water and each sachet is 2.45 gr.

## 2. Objectives of the study

The objective of this study is to evaluate the efficacy of the PEAPROSTIL 600 (FARMITALIA®) supplement composed of Serenoa Repens associated with PEA combined with alpha-blocker in the reduction of LUTS symptoms in patients with IBP. During the entire study period, any adverse events, intolerance, allergic reactions, complications related to the products used will be recorded.

### 2.1 Primary Outcomes:

1) Evaluate the efficacy of the treatment in terms of subjective improvement of urinary symptoms by performing IPPS and SF-36 questionnaires and evaluate the objective improvement of urinary symptoms by performing uroflowmetry before and during treatment (during control visits follow-up at 1,3,6 and 12 months) by evaluation of the ultrasound post-voiding residue, comparing patients receiving combined therapy with tamsulosin+peaprostil (Arm 1) with patients receiving monotherapy with tamsulosin (Arm 3).

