#### 6. Sample size and statistical analysis of the data

A total of 250 patients will be recruited. The sample analysis was performed by the "GF Ingrassia" Department of Medical, Surgical Sciences and Advanced Technologies of the University of Catania. In particular, the design foresees a 1:1:1 randomization process in 3 arms. Expect a difference of at least 2 points in IPSS and Qmax and a standard deviation of 4, as described in previous studies (Morgia et al., 2014; Alcaraz et al., 2016), it is necessary to enroll 250 patients to obtain a power 90% statistic at a significance level of 0.05.

The statistical analysis of the data collected during the study, according to an intention-to-treat procedure, will be performed using statistical software such as IBM SPSS statistics version 23.0. The variables that will be collected in order to evaluate the efficacy of the therapy will be: chronological age, weight, BMI, smoking, diabetes, PSA, IPSS, Postvoiding Residual, Qmax, QMed, Voided volume, SF-36 score. A descriptive analysis of the patients included in the three arms will be performed using the appropriate frequency measures and indices of central tendency and dispersion. Considering one pair of the three arms at a time (1 vs. 2; 1 vs. 3; 2 vs. 3), the qualitative variables will be compared using the chi-squared test; the quantitative variables will be

compared using Student's t-test. The level of significance will be set at  $p < 0.05$ . For the variables that will be significant in the univariate analysis, multivariate analyzes will be performed using appropriate regression models to control for the effect of the covariates.

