#### 7. Duration of the study

The duration of the study will be 1 year. The enrollment of patients will take place for 1 year, the follow-up will be concluded 1 year after enrollment. A preliminary statistical analysis will be performed with the data obtained at 3 and 6 months. The final analysis will be conducted upon completion of the study.

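### The primary objective (Arm 1 vs Arm 3) fixes no primary variable, visit, success rule or multiplicity control, so the stated 5% level and 90% power attach to no defined result

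*Combined protocol and SAP*

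**What the plan says.** Section 2.1 gives a single primary objective, comparing Arm 1 (tamsulosin plus PEAPROSTIL 600) with Arm 3 (tamsulosin alone). Efficacy is to be assessed "by performing IPPS and SF-36 questionnaires and evaluate the objective improvement of urinary symptoms", the latter by "performing uroflowmetry before and during treatment (during control visits follow-up at 1,3,6 and 12 months) by evaluation of the ultrasound post-voiding residue". No measure and no visit is placed ahead of the others.

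Section 6 sizes the trial on two variables: "Expect a difference of at least 2 points in IPSS and Qmax and a standard deviation of 4". It concludes that "it is necessary to enroll 250 patients to obtain a power 90% statistic at a significance level of 0.05". Its list of efficacy variables mixes outcomes with covariates such as age and smoking, ends with "Qmax, QMed, Voided volume, SF-36 score", and marks none as primary. All quantitative variables are compared between every pair of arms by Student's t-test at p < 0.05, with no visit named. A second step then depends on the first: "For the variables that will be significant in the univariate analysis, multivariate analyzes will be performed using appropriate regression models". The covariates are not listed, and the text does not say whether the t-test or the regression decides.

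Section 7 states that "A preliminary statistical analysis will be performed with the data obtained at 3 and 6 months" and that a final analysis follows at study completion. It gives no primary visit and no rule for the significance level across these analyses. Multiplicity is not mentioned anywhere.

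A smaller gap concerns SF-36. Section 5.4 names it at each follow-up visit, but the T0 list in Section 5.2 refers only to an unnamed quality-of-life instrument, so change from baseline in SF-36 may not be available.

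**The concern.** A primary objective has to identify the result that will decide it. Here at least four measures at four visits qualify, and two opposite success rules fit the text equally well.

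- **Any one result counts.** The 5% level of Section 6 then applies to each test but not to the conclusion, and the variable and visit can be picked after the data are seen.
- **All results must succeed.** Error is then controlled, but the stated 90% power does not apply to that requirement.

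Under either rule, the aim in Section 8 of reaching dependable conclusions about efficacy is not secured. Once the data have been seen, a choice of endpoint can no longer be made credibly.

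**Working it through.** **Inputs from the plan.** Difference 2, SD 4 (so 2/4 = 0.5 SD) for IPSS and Qmax; alpha 0.05; power 90%; 250 patients allocated 1:1:1, i.e. 250/3 ≈ 83 per arm (Sections 3 and 6). Four follow-up visits (Section 2.1).

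**Inputs assumed.** The documents give no correlations and no sidedness. I take two-sided tests (2.5% in the direction favouring Arm 1), correlations of 0.2-0.6 between outcomes and 0.5-0.8 between visits, SF-36 as one score, and uroflowmetry as Qmax only.

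**1. The plan's own figure.** For a two-sided test of one variable in one pair of arms:

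n per arm = 2(1.960 + 1.282)² × 4²/2² ≈ 84.1, rounded up to 85; 3 × 85 = 255.

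This is close to 250. A one-sided 0.05 test gives 69 per arm (207 in all) and does not fit. The t-test solution is 85.03 per arm. At 83 per arm, power is 89.3% by the t-test and 89.6% by the normal approximation. So 250 matches one endpoint in one comparison with no adjustment.

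**2. False-positive risk if any one result counts.** With k independent tests, the risk favouring Arm 1 is 1 − 0.975^k. For correlated tests, 400,000 sets of normal test statistics were simulated with no treatment effect. The correlation between two tests was the outcome correlation times the visit correlation. The simulation counted any z > 1.96 (favouring Arm 1) and any |z| > 1.96 (either direction).

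**3. Power if all must succeed.** Patient-level simulation with t-tests, 83 per arm and a true effect of 0.5 SD on every test.

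| Tests | Independent, favouring Arm 1 | Correlated, favouring Arm 1 (nominal 2.5%) | Correlated, either direction (nominal 5%) | Power if all must succeed |
|---|---|---|---|---|
| IPSS and Qmax, one visit (2) | 4.9% | 4.4-4.9% | 8.8-9.7% | 81-83% |
| Four outcomes, one visit (4) | 9.6% | 7.2-9.0% | 14-18% | 67-75% |
| IPSS and Qmax, four visits (8) | 18.3% | 9.6-14.6% | 19-28% | 54-69% |
| Three outcomes, four visits (12)* | 26.2% | 12.7-20.5% | 25-39% | not computed |
| Four outcomes, four visits (16) | 33.3% | 15.2-25.7% | 30-48% | 34-57% |

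*Uroflowmetry and residual urine read as one measure.

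**4. Sensitivity.** With outcome correlations of 0-0.8 and visit correlations of 0-0.9, the risk favouring Arm 1 is 7-18% for IPSS and Qmax over four visits and 10-33% for all 16 tests. If visit correlation decays with distance (adjacent visits 0.5-0.8, outcomes 0-0.7), IPSS and Qmax over four visits give 10-16%. Repeating step 2 with t-tests on simulated patients (83 per arm) gives 9.9-14.6% for IPSS and Qmax over four visits and 15.1-25.7% for all 16.

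The power column is optimistic outside IPSS and Qmax, because the plan gives 0.5 SD for those two only. If SF-36 and residual urine had an effect of 0.3 SD, all four outcomes at one visit would succeed together in 24-34% of trials.

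**The case against.** The strongest reply is that the inflation figures rest on a success rule the plan never states. If IPSS and Qmax both had to be significant at one fixed visit, there would be no inflation. That is true, but the plan does not say this either, and under that rule the 90% power fails. The figures are conditional and should be read that way. The 10-15% band also depends on the visit correlations; the wider range is 7-18%.

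Second, Section 7 calls the 3- and 6-month analyses preliminary, so a fair reader might place the decision at 12 months. On that reading the IPSS and Qmax figure is 4-5%. However, Section 7 says only when the final analysis takes place. It does not restrict that analysis to 12-month data, and Section 2.1 lists all four visits.

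Third, sizing IPSS and Qmax separately gives the same number, because both have the same assumed effect. This stands: naming two variables in the sample size is not in itself a contradiction. It becomes one only if both must succeed. The gap between 89% and 90% power is trivial.

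Fourth, the baseline quality-of-life instrument may simply be SF-36. That is possible, and a wording change settles it. Comparisons involving Arm 2 are already secondary under Section 2.2 and are not part of this defect.

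Finally, ordered testing is free only for the first test. This also stands, and the cost is stated under the fix.

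**Conclusion.** The concern holds and should be corrected before any outcome data are seen. The omission of a primary variable, visit, success rule and multiplicity control is plain from Sections 2.1, 6 and 7 and needs no assumption. Its size does. If either of IPSS and Qmax is enough, the risk of a false claim for Arm 1 is roughly twice the nominal 2.5% at one visit and four to six times it over four visits. With all four measures it is higher still. These multiples rest on two-sided testing and the assumed correlations. The sample size supports one endpoint in one comparison, and the objective should be written to match.

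**What to change.** **Section 2.1.** Suggested text: *Primary endpoint: change in IPSS from T0 to T4 (12 months), Arm 1 vs Arm 3, two-sided 0.05. If significant, change in Qmax, change in post-void residual and one named SF-36 score at T4 are tested in that order, each at two-sided 0.05, stopping at the first non-significant result.* IPSS at T4 fits the stated aim of reducing symptoms. The sponsor may choose another endpoint, visit or order if it is fixed before data are seen.

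**Section 6.** State that the t-test decides each of these comparisons, and that one regression with covariates listed in advance is reported as supportive whatever the t-test shows. A single prespecified regression could decide instead, but not one run only after a significant t-test. Tie the sample size to the primary endpoint in Arm 1 vs Arm 3 (about 83 per arm, about 89% power before dropout). Say whether the SD of 4 refers to change or to the T4 value, and how missing T4 values enter the intention-to-treat analysis. Report other variables, other visits and Arm 2 comparisons as supportive, with 95% confidence intervals.

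**Section 5.2.** Name SF-36 at T0, or state that it is compared at T4 without baseline.

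**Section 7.** State that the 3- and 6-month analyses are supportive and that the primary test is made once, in the final analysis.

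**Cost.** Mostly wording, plus SF-36 at T0 if it is not already collected. The primary test needs no extra patients; a Bonferroni split over four outcomes (alpha 0.0125) would need about 116 per arm.

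- T4 is the visit most exposed to dropout, and the plan states no allowance. An assumed loss of 10% leaves 74.7 per arm and 86% power; 20% leaves 66.4 and 82%.
- The chance of passing all four ordered tests equals the all-must-succeed figure: 67-75% at 0.5 SD each, or 24-34% with 0.3 SD for residual and SF-36, before dropout.
- An isolated significant result at another visit, or later in the order, would no longer count as meeting the primary objective.
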